## **1. Abbreviations and Definitions**

VLNC: Very low nicotine content

CO: Carbon monoxide

BPM: Beats per minute

MINI: Mini International Neuropsychiatric Interview

IVR: Interactive Voice Response

CPT: Cigarette Purchase Task

## **2. Introduction**

This document will serve as the Statistical Analysis Plan for the University of Vermont Tobacco Center of Regulatory Science study of extended exposure to cigarettes with very low nicotine content conducted with pregnant women. It describes the planned statistical analysis for evaluating the chronic effects of very low nicotine content (VLNC; 0.4 mg/g tobacco averaged across menthol and non-menthol products) research cigarettes (Spectrum cigarettes manufactured by 22nd Century Group, Clarence, NY). Assignment to a menthol or non-menthol product will be based on a participant's reported usual brand. Details for the proposed analysis of the primary, secondary, and exploratory endpoints are provided.

## **3. Trial Objectives**

The primary objective of this study is to evaluate the effects of extended exposure to VLNC cigarettes in socioeconomically disadvantaged pregnant women. Parallel studies have been conducted with socioeconomically disadvantaged women of reproductive age, opioid-maintained smokers, and smokers with affective disorders. The study will use a two-condition, parallel-groups design. After a baseline period in which daily smoking rate and other baseline characteristics are assessed, participants will be randomly assigned to one of two cigarette conditions for the 12-week experimental period, namely VLNC cigarettes (0.4 mg/g tobacco) or each participant's reported usual brand (UB).

## **4. Trial Design**

This is a randomized, multi-center, parallel-groups design. Sample size is based on 90 participants completing the entire study protocol. The VLNC cigarettes to be used throughout this trial are as follows:

Table 1. Description of cigarettes used in this trial.

Condition	TPMF Code	Type*	Specifications Nicotine Yield	Specifications Tar Yield	Specification Range for Nicotine Yield	Specifications Nicotine Content
2	NRC102	VLN	0.03 ± 0.01	9 ± 1.5	0.02 - 0.04	0.37 ± 0.01
2	NRC103	VLN-Men	0.03 ± 0.01	9 ± 1.5	0.02 - 0.04	0.39 ± 0.00
3	N/A	Usual Brand	N/A	N/A	N/A	N/A
3	N/A	Usual Brand-Men	N/A	N/A	N/A	N/A

*Legend:	
VLN	Very Low Nicotine
VLN-Men	Very Low Nicotine-Menthol

Usual brand cigarettes will serve as the comparator of interest, unless otherwise specified.

#### 4.1. Condition Assignment/Randomization

The study consists of two baseline assessments, separated by one to three weeks, 12 weeks of extended exposure to research or usual brand cigarettes, with assessments completed weekly, an abstinence assessment the day following the Week 12 visit and a final assessment 30 days after completing the study.

Participants will be randomly assigned to one of the two conditions, with randomization stratified by site and menthol preference. The lead statistician will create a randomization schedule for each site, amounting to at least 150% of expected enrollment at that site. The excess randomization codes will be used in the event that a site will have to enroll extra participants due to unexpectedly slow enrollment at another site.

The assumptions needed to generate the randomization schedule for this study are summarized in Table 2. The final randomization sequences were generated January 18, 2022. There are two major types of assumptions: 1) the proportion of participants recruited from each site, and 2) the proportion of recruited participants at each site who smoke menthol/non-menthol cigarettes. The recruitment goal for this study is 111 people. A sample size of 90 completers is proposed to test the primary aim in Study 2. Anticipating 15% attrition, and five pilot participants (3 at UVM, 2 at the University of Kentucky [UK]), 111 participants will be enrolled across both sites (74 at UVM, 37 at UK).

Participants will be recruited from the University of Vermont (UVM) and the University of Kentucky (UK). In the acute exposure portion of this project, 19% of the smokers at UVM used menthol and 81% smoked non-menthol cigarettes. Based on data from previous studies conducted at UK, menthol was assumed to be the preferred flavor for 33% of the UK participants. For ease of calculations, the UVM estimate was rounded to 20% menthol smokers.

The assumption for the extended exposure study is that 67% of the smokers recruited will come from UVM, with the remaining 33% from UK. From this it follows that 74 participants will be recruited at UVM ( $=0.67*111$ ) and 37 at UK ( $=0.33*111$ ).

The estimated numbers of menthol and non-menthol smokers to be recruited were calculated as the products of the proportions of menthol and non-menthol smokers and the recruitment numbers. For UVM, this was calculated as  $0.20*74$  or 15 menthol smokers, and  $0.80*74$  or 59 non-menthol smokers, rounded to the nearest integers. For UK, this was calculated as  $0.33*37$  or 12 menthol smokers, and  $0.67*37$  or 25 non-menthol smokers, rounded to the nearest integers. In order to allow an oversupply of randomization codes, the number of codes generated is to be at least 150% of the recruitment goal. To conform to the number of participants in each randomization block (which is 4) the number of randomization codes used is a multiple of 4. Thus, in order to allow for 15 UVM menthol smokers, 24 randomization codes were generated ( $15*1.5 = 22.5$ , next higher multiple of 4 = 24). In order to allow for 59 UVM non-menthol smokers, 92 randomization codes were generated ( $59*1.5 = 88.5$ , next higher multiple of 4 = 92). In order to allow for 12 UK menthol smokers, 20 randomization codes were generated ( $12*1.5=18$ , next higher multiple of 4 = 20). In order to allow for 25 UK non-menthol smokers, 40 randomization codes were generated ( $25*1.5 = 37.5$ , next higher multiple of 4 = 40). Based on the calculations above, a total of 176 randomization codes were initially generated for this study.

Table 2. Assumptions used in developing the randomization schedule.

	Menthol	Recruitment Percent	Total Recruitment n	Menthol Recruitment n	Menthol Randomization n	Non-Menthol Recruitment n	Non-Menthol Randomization n	Randomization Goal (150%)	Final Randomization n
UVM	20%	67%	74	15	24	59	92	111	116
UK	33%	33%	37	12	20	25	40	56	60
Total			111	27	44	84	132	167	176

#### **4.2. Sample Size**

Sample size was determined using power analysis for hypothesis tests related to the Primary Aim of Study 2, specifically to detect a significant difference between the VLNC condition and the UB condition in the primary endpoint, cigarettes per day (CPD), at the end of the trial. Effect size estimates were based on our previous studies of normal nicotine cigarettes (NNC) and VLNC use in disadvantaged women of childbearing age and estimates of CPD in our completed study on smoking topography in pregnant women and women of childbearing age. In that study, pregnant women smoked an average of 12.1 CPD, while preliminary data from our trial of women of childbearing age suggest a decrease of 5 CPD in women smoking VLNC compared to those smoking NNC. A sample size of 45 completers per condition will provide 80% power to detect statistically significant differences in smoking rate, with significance level alpha = 0.05.

### **5. Study Populations**

#### **Inclusion/Exclusion Criteria**

##### Inclusion Criteria:

- 1) Pregnant women ages 21-44 years who have < an Associate's degree
- 2) Have appropriate equipment to complete face-to-face video assessments. For participants who do not have smartphone, research staff will explore potential alternative plans (e.g., provide inexpensive Android phone)
- 3) Have a positive urine cotinine dipstick
- 4) Be without current (within the past year) serious mental disorder that would interfere with study results or completion as determined by the licensed medical professional or PI
- 5) Be sufficiently literate to complete the research-related tasks;
- 6) Be in good physical health without serious illness or change in health or medication in the past three months as determined by the licensed medical professional at each site;
- 7) Report no significant use of other tobacco or nicotine products within the past month (more than 9 days in the past 30).
- 8) Provide verification of gestational age  $\leq$  25 weeks from OB/GYN at time of enrollment

Exclusion Criteria:

- 1) Exclusive use of roll-your-own cigarettes;
- 2) Planning to quit smoking in the next 30 days;
- 3) A quit attempt in the past 30 days resulting in greater than 3 days of abstinence;
- 4) Currently taking anticonvulsant medications including:
  - a. Phenytoin [Brand Name: Dilantin]
  - b. Carbamazepine [Brand Name: Tegretol, Carbatrol, Equetro, Epitol]
  - c. Oxcarbazepine [Brand Name: Trileptal]
  - d. Primidone [Brand Name: Mysoline]
  - e. Phenobarbital
- 5) Currently seeking smoking cessation treatment;
- 6) Have used nicotine replacement, bupropion or other pharmacotherapies as cessation aids in the past month (bupropion will be allowed for treatment of depression);
- 7) Symptoms of psychosis, dementia or mania;
- 8) Suicidal ideation in the past month (score > 1 on the Beck Depression Inventory question 9 or endorse question 4 and/or 5 on the Mini International Neuropsychiatric Interview (MINI) suicide subscale);
- 9) Reporting a plan or attempt to commit suicide, which is assessed on question A3g of the MINI Neuropsychiatric Interview Major Depressive Episode Module. Thoughts of suicide without an intent or plan is not an exclusion criterion;
- 10) Suicide attempt in past six months (endorse question 6 on the MINI suicide subscale with suicide attempt in the past six months);
- 11) Participation in another research study in the past 30 days
- 12) Reporting symptoms of COVID-19
- 13) Positive toxicology screen for any of the following drugs will be grounds for exclusion: cocaine, opiates, methadone, oxycodone, buprenorphine, benzodiazepines, barbiturates, amphetamines, methamphetamines, MDMA and PCP.
  - a. Marijuana will be tested but will not be an exclusionary criterion. Participants will be discouraged from smoking marijuana during the study.
  - b. Participants with valid prescriptions for opiates, benzodiazepines, barbiturates, amphetamines will not necessarily be excluded.
  - c. Participants failing the toxicology screen will be allowed to re-screen once, if they are still eligible for the screening at the time of the re-screen. These participants will need to be re-consented before being re-screened to ensure they have received adequate informed consent.
- 14) Systolic blood pressure < 80 or ≥ 140 mmHg;
  - a. Participants failing for blood pressure will be allowed to re-screen once.
- 15) Diastolic blood pressure < 50 or ≥ 90 mmHg;
  - a. Participants failing for blood pressure will be allowed to re-screen once.
- 16) Breath CO > 50 ppm;
- 17) Heart rate greater than or equal to 110 bpm or less than 45 bpm;
  - a. Participants failing for heart rate will be allowed to re-screen once.

Women under age 21 are excluded because they cannot legally buy cigarettes. Those with unstable medical, psychiatric, or medication conditions (condition and/or medication changes in the past three months) are excluded as these symptoms could affect a participant's ability to complete the study. Examples include but are not limited to the following: angina, stroke, heart attack which occurred since phone screening, blood clots in the arms or legs for which the individual is undergoing active medical treatment, cancer requiring active chemotherapy or radiation therapy, severe shortness of breath caused by conditions such as uncontrolled asthma, COPD, or arrhythmia, active untreated infection such as pneumonia, active untreated endocrine disorder such as hyperthyroidism. Individuals with baseline CO readings greater than 50 ppm, those with blood pressure or heart rate readings that are out of range (acceptable ranges are systolic: 80-139 mmHg; diastolic: 50-89 mmHg; heart rate: 45-109 bpm) and anyone who has attempted suicide in the past 6 months will be excluded from the study for safety concerns. Individuals who smoke 'roll your own' cigarettes exclusively will be excluded from the study because we will be unable to standardize their baseline smoking behavior. Individuals who have recently participated in a research study will be excluded as participation may have changed their smoking behavior, which may preclude a stable smoking baseline. Because participants are required to complete portions of the protocol independently, they will need to be able to independently read and comprehend the study materials.

### **5.1. Full Analysis Population**

Participants will be randomized to a study condition after the completion of the first baseline visit in order to allow study staff adequate time to compile the supply of the appropriate cigarettes sufficient to cover 100% of their reported baseline CPD. Thus, randomization begins after the first baseline visit and is completed at the second baseline visit when participants receive research or usual brand cigarettes. For data analyses, the full analysis population will include participants completing the entire randomization process. Participants will be analyzed based upon the dose to which they were assigned, regardless of protocol violations and/or compliance to condition assignment. Our primary results will be based on this intention-to-treat population (i.e. randomized to a condition and received cigarettes).

### **5.2. Per-Protocol Population**

A separate per-protocol population will also be used for this study, with the results from these analyses compared to those of the full analysis population in order to examine whether missing data affects the outcomes of interest. Participants who complete the 12-week protocol will represent the per-protocol population.

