## **7.3. Primary Endpoint Analysis**

### **7.3.1. Primary Analysis**

The primary endpoint is CPD during Week 12, compared to the CPD at baseline. While the primary outcome is the mean total CPD, consisting of both study and non-study cigarettes, the analyses will be repeated examining only the CPD contributed by study cigarettes. CPD will be computed as the mean CPD calculated on a weekly basis. Data analysis will use repeated measures analysis of variance, with two conditions and two time points (baseline and Week 12). In addition, the analysis model will include a random effect for site, a random

participant effect and random error (within-subject error). Variance parameters will be estimated using restricted maximum likelihood method with the Satterthwaite approximation.

Because CPD will be measured weekly, additional analyses will be performed including data collected at all time points. The analysis will be conducted in a manner similar to that described above, with the exception that there will be 13 time points: baseline and Weeks 1 through 12. For these analyses, the variance-covariance structure will be specified as first-order autoregressive.

Additional outcomes include the CPT, breath CO level, urinary cotinine concentration, and nicotine dependence and withdrawal scores. These will be examined in a manner similar to that described above for CPD. Natural log transformations will be performed as needed so that ANOVA model assumptions of normality and equal variances hold. Geometric means in original units will be calculated as well. Note that not all outcomes are assessed at weekly in-person visits. The time points at which each outcome is assessed is described in Section 6.

Finally, several assessments will be made at baseline as well as at the abstinence visit, which occurs the day following the Week 12 assessment. At this visit, measures of craving and withdrawal will be completed. The analysis will be similar to that described above for the CPD comparing baseline CPD to that reported at the end of the trial. The analysis will deviate from that described only in the timing of the tasks, with the time points consisting of the baseline and the abstinence visits, rather than the baseline and Week 12 visits reported above.

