## **7.6. Missing Data**

We will test the pattern of missing values using Little's MCAR test, and, assuming that the data are missing at random, we will employ statistical procedures that are based on maximum likelihood estimates, which will allow the inclusion of all subjects without imputation of missing values. The maximum likelihood approach estimates the parameter values that would maximize the probability of observing the data collected. In the event of missing variables, the likelihood for a given individual is the probability of observing the non-missing variables. Thus, the maximum likelihood approach allows the use of data from participants for the time period for which data is available, but not for time periods for which the data is missing. This procedure uses information from earlier time periods to estimate the effects of later time periods, while also accounting for the uncertainty of the projection in the computation of standard errors and test statistics. While maximum likelihood estimation is considered superior to imputation methods for the treatment of missing data in clinical trials, additional analyses will be conducted using several imputation methods to test the sensitivity of these results. Imputations methods will include, but not be limited to, last observation carried forward and multiple imputation with the Markov Chain Monte Carlo (MCMC) method carried out in PROC MI in SAS.

In the case of non-random missing data, we will conduct sensitivity analyses using

multiple imputation with the Markov Chain Monte Carlo (MCMC) method carried out in PROC MI in SAS. If missing data is associated with experimental condition, we will conduct multiple imputation for each experimental condition. At least 10 imputed data sets will be generated, with the experimental-condition effect being assessed in each imputed data set. A final single assessment of experimental condition differences will be obtained from combining the results across the imputed datasets using PROC MIANALYZE in SAS. The results of these analyses will be compared to the primary analysis to evaluate the robustness of our conclusions.

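### Agreement between the 12-week completers (labelled per-protocol) and the full analysis cannot show that missing data are harmless, because both rest on essentially the same Week 12 CPD values

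*SAP*

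**What the plan says.** SAP 5.1 bases the main results on everyone randomized and supplied: "Our primary results will be based on this intention-to-treat population (i.e. randomized to a condition and received cigarettes". They are analysed as assigned, "regardless of protocol violations and/or compliance to condition assignment".

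SAP 5.2 defines the second set in one sentence: "Participants who complete the 12-week protocol will represent the per-protocol population". It names no condition on product adherence, visit attendance or completeness of the daily IVR reports. The only stated purpose is that its results are "compared to those of the full analysis population in order to examine whether missing data affects the outcomes of interest".

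The primary model in SAP 7.3.1 is a repeated measures analysis "with two conditions and two time points (baseline and Week 12". A supplementary CPD analysis follows, in which "there will be 13 time points: baseline and Weeks 1 through 12".

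SAP 7.6 handles missing values by likelihood under missing at random (MAR). A participant's data count for the periods observed, "but not for time periods for which the data is missing". The section adds: "This procedure uses information from earlier time periods to estimate the effects of later time periods". It also plans Little's test, last observation carried forward (LOCF) and MCMC multiple imputation.

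**The concern.** A check on missing data is useful if its result changes when missing data cause harm. In the primary model the only earlier period is baseline. A woman who leaves before Week 12 therefore contributes her baseline CPD and nothing else, and almost all Week 12 information in the full analysis comes from the women who make up the completer set. If the women who leave would have smoked more at Week 12 than their baseline predicts, neither analysis can see it.

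The documents make such dropout plausible. The protocol's background section expects that very low yields may bring more withdrawal and poorer acceptability and compliance. Its withdrawal rules remove a participant whose breath CO more than doubles from baseline or exceeds 50 ppm, and CO is not in the CPD model.

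The label adds a second risk. Readers take a per-protocol result to mean women who used the assigned product. Here a VLNC participant who smoked mainly her own brand for 12 weeks would be included. A report that the intention-to-treat and per-protocol results agree could be read as robustness to both dropout and non-adherence, and would establish neither.

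**Working it through.** **Planned attrition, reproduced.** Protocol (Study 2 Recruitment) and SAP 4.1 give 90 completers, 15% attrition and 5 pilots. 90 / 0.85 = 105.9, rounded up to 106; 106 + 5 = 111, as stated. About 106 - 90 = 16 randomized women would lack a Week 12 value.

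**Inputs from the documents.** Baseline 12.1 CPD and effect -5 CPD (SAP 4.2); 53 per arm (106 / 2, 1:1 allocation).

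**Assumptions.** The documents give no SD and no correlation. SD 8.46 is the value at which 45 per arm has about 80% power for 5 CPD, two-sided 0.05. The correlation rho between baseline and Week 12 is varied over 0.4, 0.6 and 0.8. The site effect is omitted.

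**Why the two analyses are tied together.** Within an arm, write A for the baseline mean of all women, C for that of completers, D for that of dropouts, and d for the dropout proportion. In the two-point model with equal variances, the likelihood estimate of the Week 12 mean is (completers' Week 12 mean) + rho × (A - C). Subtracting A gives

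full change - completer change = -(1 - rho)(A - C), where A - C = d(D - C).

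The gap depends only on how dropouts differed at baseline. Their unseen Week 12 smoking does not enter. With rho = 0.6 and d = 0.15:
- equal baselines: gap 0
- dropouts 5 CPD higher at baseline: 0.4 × 0.15 × 5 = 0.30 CPD

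**Shared bias with no gap.** Suppose VLNC dropouts go back to their baseline rate and do not differ from completers at baseline. At 15% VLNC dropout the true effect is -5 × 0.85 = -4.25; at 25% it is -5 × 0.75 = -3.75. Both analyses have expectation -5.0 and an expected gap of 0.

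**Simulation.** 1,500 trials per setting, true effect -5. Usual-brand dropout is random. VLNC dropout is random, or rises with baseline CPD, or rises with Week 12 CPD. Estimates are the condition-by-time contrast; gap is the mean absolute difference between the two analyses.

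| Dropout VLNC/UB | rho | VLNC dropout driven by | Full | Completers | Gap |
|---|---|---|---|---|---|
| 15%/15% | 0.6 | chance | -4.94 | -4.95 | 0.22 |
| 15%/15% | 0.6 | baseline CPD | -4.92 | -4.38 | 0.54 |
| 15%/15% | 0.6 | Week 12 CPD | -5.86 | -5.54 | 0.35 |
| 25%/5% | 0.6 | baseline CPD | -5.05 | -4.18 | 0.87 |
| 25%/5% | 0.6 | Week 12 CPD | -6.42 | -5.90 | 0.53 |
| 15%/15% | 0.4 | baseline CPD | -4.92 | -4.13 | 0.80 |
| 15%/15% | 0.4 | Week 12 CPD | -6.18 | -5.86 | 0.43 |
| 15%/15% | 0.8 | baseline CPD | -4.99 | -4.73 | 0.27 |
| 15%/15% | 0.8 | Week 12 CPD | -5.45 | -5.23 | 0.22 |

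At rho = 0.6 the standard error of the full estimate is about 1.5, and the two estimates correlate at about 0.98. At 15%/15% the 0.35 gap under harmful dropout lies inside what purely random dropout produces (95th percentile 0.56). In every pair of rows the gap is larger when the full analysis is about unbiased than when both analyses are biased, though at rho = 0.8 the two gaps are close. An independent rerun of these settings reproduced the pattern, with estimates within about 0.1 CPD.

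**The case against.** **The two analyses need not agree.** A reader might infer that they always will. They will not: when dropout depends on baseline CPD, a situation covered by the MAR assumption of SAP 7.6, they separate by 0.54 to 0.87 CPD at rho = 0.6. In the 13-point model dropouts also contribute their earlier weeks, and SAP 5.2 speaks of outcomes in general. This stands. The comparison carries some information about dropout linked to observed CPD. It carries almost none about dropout linked to unseen Week 12 CPD.

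**SAP 5.2 is not the only check.** A reader might infer that the plan has no other missing-data analysis. SAP 7.6 has several, including imputation by condition if missingness is related to condition. That limits the harm, but does not repair the inference in 5.2. The method that 7.6 names for non-random missingness is again MCMC multiple imputation, which as specified assumes MAR.

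**Same Week 12 values is an approximation.** Completing the protocol is not defined by having Week 12 IVR data, so membership and data could differ for a few women.

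**Adherence is partly covered.** Adherence is a secondary endpoint, and SAP 7.3.1 repeats the CPD analysis on study cigarettes alone. A reader might infer that an adherence-restricted analysis is required, or that a simple cut-off on non-study cigarettes would do. The documents do not support either. Women who quit stay enrolled, and a non-study share of zero cigarettes is undefined. The IVR data are self-report. For a usual-brand woman a non-study cigarette may be the identical product. The study-cigarette analysis changes the outcome rather than the population, so it does not justify the label either.

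**Conclusion.** The point holds in a limited form. Agreement between completers and the full analysis is not evidence that missing data are harmless, and a larger gap is not evidence that the full analysis is wrong. At 15% dropout per arm and rho = 0.6, the full analysis can be off by 0.86 CPD (-5.86 against -5) with a mean gap of 0.35. It can be close to correct with a gap of 0.54.

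These sizes rest on an assumed SD, correlation and dropout mechanism, none of which the documents give. Across correlations of 0.4 to 0.8 at 15% per arm, the bias of the full analysis under Week 12-driven dropout runs from 1.18 (6.18 - 5) down to 0.45 (5.45 - 5) CPD. The structural argument needs none of these figures. The primary analysis and its population are unaffected; what needs correcting is the label and the inference drawn from the comparison.

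**What to change.** 1. In SAP 5.2, rename the set completers, and say whether completion requires Week 12 IVR data.
2. Delete the statement that the comparison examines the effect of missing data, or limit it to describing differences linked to baseline or earlier CPD.
3. Refer the missing-data question to SAP 7.6. For the non-random case, specify a delta-adjusted or reference-based imputation there, with the shifts or reference fixed before data are seen by condition.
4. If a per-protocol set is still wanted, define it from the daily IVR adherence data. State rules for women smoking zero cigarettes and for usual-brand women, and report it only as a supportive, non-randomised analysis.

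The cost is SAP wording and one additional imputation program, plus one derived flag if item 4 is taken up. No new data are needed.
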